6.2. Assessments

Refer to the SOA ([Appendix 1](#)) for the main study, and [Appendix 3](#) for the OLE for details regarding the timing and frequency of study assessments. Laboratory evaluations, muscle function tests and spirometry assessments should be performed prior to infusions.

6.2.1. Vital Signs (including Weight)

Vital signs to be collected include; heart rate, blood pressure, respirations and temperature:

- Heart rate should be collected as beats/min
- Respiration rate should be collected as breaths per minute
- Systolic and diastolic blood pressure should be collected from subjects in seated position (mmHg)
- Temperature should be taken using any standard method and captured as °F or °C

Weight is collected during screening, and every 12 weeks (or within 14 days prior) after Day 0. Height is collected as ulna length measurement by respiratory technician only, during PFT visits. For subjects that enter the study at age 18 or turn 18 during the study, the last recorded ulna length/height will be used for the remainder of the study.

6.2.2. Physical Exam

A full physical exam is required at screening, throughout the treatment period, and at EOS and ET. Refer to the SOA (Appendix 1) for details.

6.2.3. Laboratory Evaluations

Details regarding sample collection, preparation and transport can be found in the central lab manual.

6.2.3.1. Central Laboratory Evaluations

The following labs will be evaluated by a central laboratory in accordance with the SOA ([Appendix 1](#)):

The total amount of blood to be drawn for routine central laboratory assessments is in [Appendix 2](#). The max total for any blood draw visit is about 1.8 tablespoons (26ml/visit). An additional 1.4 teaspoons (20 ml) will be drawn in the event of an immunogenic reaction (see [Section 6.2.3.2.3](#) for more detail).

Local guidance and regulations on total blood volume to be drawn takes precedence over general recommendations.

Glomerular Filtration Rate (GFR) is calculated and resulted by the central lab contracted by the Sponsor for Exclusion Criteria 5c. For subjects 18 years old and under, the “Creatinine – Cystatin C based CKiD equation (Schwartz 2012)” is used. For subjects 19 years old and above, the “CKD-EPI cystatin C equation (Levey 2009)” is used. However, it is common for patients with DMD to have very low creatinine to the level where it is below detectable limits and a result cannot be reported. As a result, GFR may or may not be available to support the evaluation of acute kidney injury. Other tests and diagnostic tools for assessment by the investigator should be used in this instance.

Table 4: Laboratory Tests

CBC:	Chemistry Panel:
Absolute neutrophil count (ANC)	BUN
Eosinophils	Creatine Kinase
RBCs (Erythrocyte count)	Creatinine
Hematocrit %	Chloride
Hemoglobin	Magnesium
WBCs (Leukocyte count)	ALP
Lymphocytes	ALT
Monocytes	AST
Neutrophils	Bilirubin, total

Platelets	Albumin
CRP	Phosphorous
Basophils	Potassium
	Sodium
	GGT
	Calcium
	GFR
	Cystatin-C
Abbreviations: ALP = alkaline phosphatase; ALT = alanine aminotransferase; AST = aspartate aminotransferase; GGT = Gamma-glutamyltransferase; BUN = blood urea nitrogen; CBC = complete blood count; RBC = red blood cell; WBCs = white blood cells. CRP= C-reactive protein; GFR = Glomerular filtration rate	

Central lab results obtained during the screening period will be used to determine subject eligibility for participation in the trial. Central lab results will be reviewed by the investigator for clinical significance and to determine appropriate reporting of adverse events (see [Section 7.3](#)). A Central Laboratory Manual with instructions on specimen collection, processing, storing, and shipping to the central laboratory will be provided to all participating sites.

Prior to MRI, local laboratory assessments may be drawn at the discretion of the investigator. The results of any local laboratory assessments are used to evaluate if it is safe for the subject to undergo the MRI with contrast. These local laboratory results conducted prior to MRI will not be captured in the clinical database.

NOTE: Local laboratory assessments may also be used in case of Central Laboratory supply shortages or shipment delays. If local laboratory assessments are used instead of central labs, results will be entered into the clinical database, and the following points need to be considered:

- In case of local screening labs, the Investigator needs to review the results with respect to protocol specified Laboratory Inclusion Criteria for adequate renal function, adequate hematology and electrolytes parameters, and adequate hepatic function.
- For on-study laboratory assessments, only laboratory abnormalities that are considered clinically significant in the Investigator's assessment need to be reported as TEAEs, as per Protocol [Section 7.3.7](#). In such a case, if possible, the etiology of a lab abnormality should be reported as TEAE, not the abnormal lab value.
- For specialty labs collected at a local laboratory:
 - HAHA and HAHA-NA samples should be collected according to the schedule of assessments in Appendix 2 using local supplies while processing/storing these samples as described in the ICON lab manual.
 - HAHA and HAHA-NA samples may be stored at the clinical site and batch shipped to ICON at a later time

- Other specialty samples (PK and Genomics) will not be required if local labs are being used

6.2.3.2. Pharmacokinetics (PK) and Specialty Labs

Additional samples will be collected to evaluate PK, HAHA, HAHA-NA, tryptase, and genomics in accordance with the SOAs in [Appendix 1](#) and [Appendix 2](#). The central laboratory will manage the storage of these samples while analysis will be performed at a specialty lab(s).

6.2.3.2.1. Pharmacokinetics

An optional PK assessment will be performed in consenting subjects at timepoints specified in Schedule of Assessments. For subjects that re-consent under the main study of this protocol, PK assessments will continue to be optional except in the case of immunogenic reaction (see [Section 6.2.3.2.3](#) for more detail). Plasma samples will be collected for estimates of PK parameters using population PK and exposure-response analysis, if possible, according to the SOAs in [Appendix 1](#) and [Appendix 2](#). A specialty laboratory will measure plasma pamrevlumab levels using a validated assay. For the population PK analysis, it is critical to accurately record the dosing time and date in addition to the sampling collection time and date. Both pre-dose and post-dose samples are required for PK as specified in [Appendix 2](#). Pre-dose should be within 2 hours prior to the administration of study treatment and post-dose should be between 1-4 hours after administration of study treatment has ended.

6.2.3.2.2. Human Anti-Human Antibodies (HAHA)

Plasma samples will be collected for evaluation of human anti-human antibodies (HAHA), specific to the impact of neutralizing anti-drug antibodies (HAHA-NA) and the impact on immunogenicity, in all subjects according to the SOAs in [Appendix 1](#) and [Appendix 2](#). A specialty laboratory will measure HAHA titers using a validated assay.

Samples/subjects with positive/specific HAHA results will be subject to evaluation of neutralizing antibody (HAHA-NA) assays and analyses. The prevalence and duration of binding and neutralizing antibodies and the effect of these antibodies on the pharmacokinetics, pharmacodynamics markers, efficacy, and safety of pamrevlumab will be assessed.

6.2.3.2.3. Immunogenic Reactions

Any immunogenic reactions, including drug-related hypersensitivity or anaphylaxis, should have PK, HAHA, HAHA-NA and tryptase drawn within 24 hours of immunogenic reaction (anaphylactic episode). (A window of “within 24 hours of infusion” could be at any point following the reaction such as 30 minutes post-reaction but not to exceed 24 hours following reaction). This includes timepoints in which PK, HAHA, and HAHA-NA were drawn prior to the reaction as well. This will not be considered optional for the subject unless there is local consideration for total blood volume collection on the same day as a standard blood draw timepoint, which could preclude the subject from having this collection take place within 24 hours. The Tryptase sample should be drawn within 1 to 6 hours of immunogenic reaction, but all samples should at least be collected within 24 hours after the anaphylactic episode. See [Appendix 2](#) for more detail.

6.2.3.2.4. DNA for Genetic Analysis

A whole blood sample will be collected in a PAXgene blood DNA tube for DNA analysis on Day 0 before dosing for all subjects who agree to DNA analysis. This testing is optional, requires specific consent by participating subjects and subjects may refuse DNA testing. In the event that a subject later agrees to genetic testing, a blood sample may be collected as an unscheduled lab draw. Only tests for genetic loci associated with dilated cardiomyopathy (DCM) will be performed and all samples will be destroyed after testing is completed.

6.2.4. Muscle Function Test (MFT)

Performance of Upper Limb (PUL) and grip strength tests will be performed during the course of the study. PUL 2.0 Kits will be provided. The grip test should be performed using a microFET® Digital Hand GRIP Dynamometer (unless specified otherwise in limited countries). The same equipment should be used for each subject, and for the duration of the study. MFTs are to be completed by a dedicated and trained staff member(s). The same evaluator should evaluate the subject at each visit for consistency. All evaluators must be trained and pass proficiency prior to any testing. Video QC of the MFT assessments will be completed by external vendor ATOM at Screening, Day 0, Week 52, and additional visits as needed, and the videos will be evaluated by an independent reviewer to confirm the local clinical evaluator is consistently administering the MFT. Data will also be assessed by independent reviewers on an ongoing basis.

6.2.5. Pulmonary Function Test (PFT)

Standardized PFTs including ppFVC, ppPEF, FEV1 will be collected for consistency during the course of the study. The central PFT vendor will provide the SpiroSphere® to conduct these assessments. PFTs will be completed by dedicated trained staff. All staff performing PFTs must pass a proficiency test to administer the test. Data will be reviewed by independent reviewers at the central PFT vendor to validate the integrity of the data. Within a PFT session, eight attempts may be made. Only sessions with a Best Test Read (BTR) grade of Borderline or Acceptable are considered valid. The session may be repeated up to three times during the screening window. The Day 0 PFT session may also be repeated up to three times. If the test cannot be performed, or the test produces Unacceptable grade results according to the central reader during a follow-up visit, the test should be performed at the next scheduled on-site visit. Valid PFT results (Acceptable or Borderline Acceptable) must be obtained at Screening and Baseline for eligibility prior to randomization. If sessions are repeated, the last session conducted for screening, and the last session conducted for Day 0 supersede all others and are used to determine the average for baseline. The inclusion criteria requires that the average percent predicted FVC be between 45 and 85, inclusively and values may be rounded such that values between 44.5 and 85.4 are also acceptable.

6.2.6. Magnetic Resonance Imaging (MRI)

MRI (cardiac and muscle) assessments will be performed to evaluate fibrosis and to determine any changes in fibrosis score from baseline to Week 52.

- Cardiac MRIs are assessed locally at Screening for eligibility before being submitted to the central imaging vendor

- A centralized image interpretation process will be formed and will provide verifiable and uniform reader training as well as ongoing management of reader performance. This will ensure quality control of the images and their interpretation and decrease variability in image interpretations, leading to a more precise estimate of treatment effect.
- An Independent blinded Centralized Imaging Charter will be formed to interpret the MRIs. Standardization is important for the clinically used MRI measures, and is essential for the study imaging endpoints, to reduce variability, and to ensure interpretability of the results. The charter will be formed According to the FDA Guidance for Industry: “Clinical Trial Imaging Endpoint Process Standards”.

6.2.7. Duchenne Video Assessment

The Duchenne Video Assessment (DVA) tool provides a standardized way to document and assess patient quality of movement. Caregivers will follow a standardized script to video record subjects doing specific movement tasks remotely using a secure mobile application within 2 weeks prior to the clinic visits specified in the Schedule of Assessments.

Trained physical therapists will score the videos in a secure scoring dashboard using scorecards with pre-specified compensatory movement criteria. The DVA vendor is the organization that developed the DVA and will manage DVA data collection, quality, and scoring.

Caregivers will register for the study mobile application, and they will download the mobile application on an Apple (IOS 10+) or Android (5.1+) smartphone. They will be provided with an eligible smartphone if they do not have access to one. Caregivers will be provided with training materials in the study mobile application and in the study kit (materials provided to each subject and caregiver) to learn how to video record the assigned movement activities. The training materials will describe how to standardize the lighting, clothing, and set-up during the video recording and how to submit videos securely to study staff using the study mobile application. Caregivers will provide an electronic signature within the study mobile application to document training completion.

Subjects will be assigned movement tasks based on functional branching questions prior to Baseline data capture and split into two functional groups based on their Brooke score as noted below. Subjects will remain in the same subgroup (Group A or B) throughout the duration of the study.

Group A: Early Non-Ambulatory Subjects (Brooke Score 1-3)	Group B: Late Non-Ambulatory Subjects (Brooke Score 4-5)
Raise Hands Above Head (Front View and Side View) Take a T-Shirt Off and Put it Back On Eat 10 Bites Roll Over in Bed Sit Up (Shift Weight) in Bed Caregiver Choice New Ability	Eat 10 Bites Putting Arms on Armrest Reach Across Table to Grab Cell Phone Sit up (shift Weight) in Bed Caregiver Choice New Ability

The specific movement activities are detailed in the Caregiver Manual. Caregivers will be provided with study supplies, including painter's tape, tape measure, and a bed wedge.

In addition to assigned movement tasks, all subjects will complete one caregiver choice activity and new ability videos (if applicable). The caregiver choice activity is an activity that the caregiver will select prior to Baseline data capture that the subject is struggling with, and the caregiver will video record the same caregiver choice activity throughout the study. If caregivers observe the subject gaining a new ability during the study, they can video record the new ability at any time during the study in the study mobile application.

The DVA vendor study staff will monitor data collection to ensure that each video meets quality standards. If videos need to be re-recorded, caregivers will be contacted about re-recording the video.

NOTE: Belgium and China Only: Duchenne Video Assessments will be not be conducted. DVA vendor services and their mobile application will not be used in these countries. There is no alternative for the DVA. All references to DVA or the DVA vendor in the study protocol are not applicable for Belgium and China.

7. ASSESSMENT OF SAFETY

7.1. Background

Adverse event (AE) reports from investigators are the critical building blocks to the development of the safety profile of the IP. Subjects will be asked non-leading questions in general terms to determine the occurrence of AEs, according to the schedule outlined in [Appendix 1](#). In addition, all AEs reported spontaneously during the course of the study will be recorded. The investigator is responsible for ensuring that any adverse events observed by the investigator or reported by the subject as defined in the study protocol are recorded in the subject's medical record. The investigator must immediately (within 24 hours of awareness) report to the sponsor or designated safety management vendor all serious adverse events (SAEs), regardless of whether the investigator believes they are related to the study drug.

7.2. Definitions

7.2.1. Definition of an Adverse Event (AE)

An adverse event is any untoward medical occurrence in a patient or clinical investigation subject administered a pharmaceutical product and which does not necessarily have to have a causal relationship with this treatment.

An adverse event (AE) can therefore be any unfavorable and unintended sign (including an abnormal laboratory finding, for example), symptom, or disease temporally associated with the use of a medicinal product, whether or not considered related to the medicinal product

The definition of adverse events includes worsening of a pre-existing medical condition. Worsening indicates that the pre-existing medical condition (e.g., diabetes, migraine headaches and gout) has increased in severity, frequency, and/or duration, and/or has an association with a significantly worse outcome. A pre-existing condition that has not worsened during the study or involves an intervention, such as elective cosmetic surgery, or a medical procedure while on study, is not considered an adverse event.

7.2.2. Definition of a Serious Adverse Event (SAE)

A serious adverse event is any adverse event or suspected adverse reaction that results in any of the following outcomes:

- Death,
- A life-threatening AEs (i.e., if in the view of the investigator or sponsor, the subject was at immediate risk of death at the time of the event). Life-threatening does not refer to an event which hypothetically might have caused death if it were more severe,
- Inpatient hospitalization or prolongation of existing hospitalization,
- A persistent or significant incapacity or substantial disruption of the ability to conduct normal life functions,
- A congenital anomaly or birth defect, or

- Is considered a medically important event not meeting the above criteria, but which may jeopardize a subject or may require medical or surgical intervention to prevent one of the other criteria listed in this definition. Examples of such medical events include allergic bronchospasm requiring intensive treatment in an emergency room or at home, and blood dyscrasias or convulsions that do not result in inpatient hospitalization.

Please note that death is an outcome, not an event; the primary cause of death would be the adverse event.

Surgical procedures, per se, are not SAEs. The condition requiring the surgical procedure, however, may be a SAE.

Scheduled or pre-planned hospitalization or prolongation of a hospitalization due to standard of care assessments and procedures (including elective procedures) do not warrant reporting as adverse events unless resulting observations are deemed by the Investigator to meet the definition of an adverse event.

7.3. Procedures for Eliciting, Recording, and Reporting Adverse Events

7.3.1. Adverse Event Reporting Period

The safety reporting period begins after the subject has signed the informed consent and ends 60 days after the last dose of IP. SAEs that occur after signing consent but before first dose must be reported, while all AEs and SAEs be reported thereafter first dose and through 60 days after the last dose of pamrevlumab/placebo are recorded. The Investigator should notify the Sponsor of any death or other SAEs occurring after a subject has discontinued or terminated study participation that may reasonably be related to this study ([Section 7.3.5](#)).

Pregnancy reporting requirements are outlined in [Section 7.3.6](#).

Adverse events will be followed until resolved, stable, or until the subject's last study visit or subject is lost to follow-up.

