3.2.1. Study Duration

All subjects are encouraged to complete up to 27 doses of study treatment, an End of Study (EOS)/Safety follow-up visit 28 days (+/- 3 Days) and a final safety follow-up phone call 60 days (+ 3 Days) after the last dose. Subjects who discontinue the study early, for any reason, will need to come in for an early termination visit (ET) 28 days (+/- 3 Days) after the last dose and a final safety follow-up phone call 60 days (+ 3 Days) after the last infusion. If a subject withdraws from the study after randomization and prior to dosing, an ET visit and safety follow-up phone call are not required. See also [Section 4.3](#) for mandatory discontinuation reasons, and [Section 4.4](#) for procedures related to the ET.

Subjects who complete the study may be eligible for rollover into an open-label, extension study which will provide data on the long term safety and efficacy of pamrevlumab.

End of trial is defined as the date at which the last subject completes the final safety follow-up phone call.

Figure 1: FGCL-3019-093 Study Schema

Abbreviations: EOS= End of Study, ET=Early Termination

Subjects who discontinue the study early, for any reason, will complete an early termination visit 28 days (+/- 3 Days) and a final safety follow-up phone call 60 days (+ 3 days) after the last infusion.

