4.3. Subject Withdrawal Criteria

Subjects may withdraw from the study at any time, for any reason. If a subject or investigator determines subject should discontinue from treatment, the subject has the option to remain on study. If the subject remains on study, they should continue to perform on-study assessments until the end of study visit or subject terminates for one of the below reasons.

Mandatory reasons for withdrawing the subject from the study include the following:

- Any safety concern in the Investigator's opinion, that precludes further study participation
 - Pamrevlumab will be permanently discontinued in case of serious or life-threatening allergic reactions
- Major protocol deviation to inclusion/exclusion that substantially affects subject safety
- Withdrawal of Consent (reason of withdrawal should be obtained)

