6.1.3. End of Study/Safety Follow-up

All subjects enrolled will have an EOS/safety follow-up visit 28 days (\pm 3 Days) and a final safety follow-up phone call at 60 days (+3 days) after the last dose of study treatment. After the protocol-required reporting period (60 days (+ 3 Days) after the last dose), the investigator does not need to actively monitor subjects for SAEs. However, if the investigator becomes aware of an SAE/death that may be possibly related to study treatment after the protocol-required reporting period, the investigator may report the event to the Sponsor SAEs reported outside of the protocol-required reporting period will be captured within the safety database only as clinical trial cases for the purposes of expedited reporting.

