- f.) Full physical exam including chest auscultation
- g.) SAEs are collected from date of consent through EOS. AEs are collected from Day 0 through EOS. Number and percentage of bone fractures is captured from Day 0 through EOS. Bone fractures should be collected in the EDC as AEs, naming them using the specific guidelines in the electronic case report form completion guidelines.
- See [Section 7](#) for follow-up of AEs.
- h.) Concomitant medications and nondrug therapies must be reported beginning after informed consent is obtained and ending 60 days after the last treatment. Refer to [Section 5.2.2](#) for additional information on prohibited concomitant medications
- i.) HAHA, HAHA-NA and PK samples. See [Appendix 2](#) for PK, HAHA, and HAHA-NA sampling time points.
- j.) MFTs: Performance of Upper Limb (v. 2.0), and Hand Grip Test.
- k.) Local labs may be drawn prior to MRIs at the discretion of the investigator.
- l.) Vital signs (pulse, respiration, sitting BP, temperature) to be collected at every visit: within 30 minutes pre-infusion, and within 30 minutes after completion of infusion.
- m.) MFTs and PFTs are collected at screening and must be repeated prior to randomization and first infusion on Day 0. They may be conducted up to 3 days in advance of the Day 0 visit. The PFT results from both time points will be used to establish baseline values. The results from MFTs at Day 0 will be used to establish baseline.
- n.) Genetic Analysis samples will be collected in PAXgene tube; samples will be collected only from subjects who consent for this test. If subject consents to this optional sample, it may also be collected at an Unscheduled timepoint if it is not collected initially at Day 0.
- o.) Duchenne Video Assessment to be performed remotely within the interval between the prior scheduled study visit and next scheduled study visit.

- p.) If the subject is not going into the OLE, he should complete a final safety follow-up that consists of a visit at week 56 and a final safety follow-up phone call 60 days (+3 days) after the last infusion visit.
- q.) PFTs, MFTs, DVA and MRI only to be done at the early termination visit
- r.) Randomization may be performed within 2 days prior to Day 0 visit, after subject is confirmed eligible (see footnote “m”).

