### **5.3.1. Analysis Period**

#### **5.3.1.1. On-Study Period**

Unless otherwise specified, the efficacy analysis will be based on the on-study period, which is defined as from randomization to the day of last efficacy assessment for the main study period prior to first study drug infusion in the OLE period for subjects who enrolled in the OLE period; or from randomization to the last day of any efficacy assessment for subjects who didn't enroll in the OLE period.

For the safety analysis, all safety assessments beyond 60 days of last dose will be excluded from summary tables or figures.

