#### **6.6.1.1.3. Intercurrent Event Handling**

Treatment discontinuation (such as due to adverse event, lost to follow-up, withdrawal by subject, physician decision, protocol deviations, etc.): Missing data will be implicitly imputed under missing at random assumption.

Death: The worst postbaseline score of all patients in the mITT population would be used to impute all missing values due to death. Missing study day will be imputed as target day of the corresponding analysis visit.

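### For a participant who stops infusions but stays on study, the end of safety collection is contradictory, and events more than 60 days after the last dose are left out of the safety tables

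*Protocol*

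**What the plan says.** **Off drug but on study.** Protocol 4.3 allows a participant to discontinue treatment and remain; in that case "they should continue to perform on-study assessments until the end of study visit". The SAP's primary estimand follows a treatment-policy strategy (6.6.1.1.1), and PUL assessments after treatment discontinuation enter the analysis (6.6.1.1.4). SAP 3.5 and Protocol Appendix 3 admit people who complete Week 52 to the extension however many infusions they received.

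**Collection tied to the last dose.** Protocol 7.3.1: "The safety reporting period begins after the subject has signed the informed consent and ends 60 days after the last dose of IP". Sections 7.3.5 and 7.3.5.2 use the same limit for SAEs and for submitting a death on the SAE form. Section 6.1.3: "All subjects enrolled will have an EOS/safety follow-up visit 28 days" after the last dose of study treatment, and once the 60-day period is over "the investigator does not need to actively monitor subjects for SAEs". Section 3.2.1 gives the same timing.

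**Collection tied to EOS.** Footnote g of Protocol Appendix 1 says that "AEs are collected from Day 0 through EOS", with the same end point for SAEs and fractures. Footnote p of that appendix and the sampling table in Appendix 2 place the EOS visit at Week 56.

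**Reporting and analysis.** Protocol 7.3.5 leaves SAEs reported outside the required period out of the study report. SAP 5.3.1.1 says that "all safety assessments beyond 60 days of last dose will be excluded from summary tables or figures", and SAP 6.8.1 ends the treatment-emergent window at 60 days.

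**Deaths in the primary analysis.** SAP 6.6.1.1.3: "The worst postbaseline score of all patients in the mITT population would be used to impute all missing values due to death". Data missing after treatment discontinuation are handled as missing at random.

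**The concern.** The efficacy plan follows a participant who stops drug to Week 52. The safety plan, on its most explicit wording, follows him for 60 days after his last dose. EOS, the term that should join the two, has two meanings that coincide only for someone dosed through Week 52.

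Two things are at stake. The first is the safety comparison. Deaths, cardiac or pulmonary hospitalisations and fractures are counted among everyone dosed, but counting time ends early for people who stop drug. If one arm stops more often, it has less time in which to accrue counted events, and the comparison leans in its favour.

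The second is the primary analysis. The death rule works only if deaths up to Week 52 are known. A death that is not recorded as the reason for missing PUL scores would be treated as missing at random, which is more favourable than the worst observed score.

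**Working it through.** The plan gives no figure of its own on this point. Sample size and power do not depend on it.

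**Step 1. When does collection stop for someone off drug?** Take a last dose at Week 10.

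| Source | Rule | Result |
|---|---|---|
| Protocol 7.3.1, 7.3.5 | 60 days after last dose | Day 71 + 60 = Day 131 |
| Appendix 1 footnote g, EOS as in 3.2.1 and 6.1.3 | 28 days after last dose | Day 71 + 28 = Day 99 (Week 14) |
| Appendix 1 footnote g, EOS as in footnote p and Appendix 2 | Week 56 | Day 393 |

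The three rules give end dates between Week 14 and Week 56. Section 4.3 does not settle the matter, because it too refers to the EOS visit.

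**Step 2. Does the reading matter for the tables?** Suppose the site uses Week 56 and records an SAE at Week 40 in this participant. The SAE is still more than 60 days after his last dose. It lies outside the period that Protocol 6.1.3 and 7.3.1 define, so 7.3.5 keeps it out of the study report. SAP 5.3.1.1 removes it from summary tables and figures, and it is not treatment-emergent under SAP 6.8.1. The all-cause death summary in 6.8.1 states no window of its own, so the general exclusion appears to govern it as well.

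**Step 3. How much on-study time is not counted?** The inputs are the study days in the SAP visit-window tables (Week w is Day 7w + 1, Week 52 is Day 365) and the 60-day limit.

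Uncounted days = 365 − (7w + 1 + 60), or zero if negative.

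| Last dose | Day | Limit (day + 60) | Uncounted days to Day 365 | Weeks |
|---|---|---|---|---|
| Week 10 | 71 | 131 | 234 | 33.4 |
| Week 12 | 85 | 145 | 220 | 31.4 |
| Week 24 | 169 | 229 | 136 | 19.4 |
| Week 26 | 183 | 243 | 122 | 17.4 |
| Week 36 | 253 | 313 | 52 | 7.4 |
| Week 42 | 295 | 355 | 10 | 1.4 |
| Week 44 | 309 | 369 | 0 | 0 |

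The gap closes when 7w + 61 reaches 365, that is at w = 304/7 = 43.4. On the two-weekly grid, every last dose at Week 42 or earlier leaves a gap.

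**Step 4. Is vital status to Week 52 secured?** Protocol 7.3.5.2 has the investigator report a fatal event to the medical monitor, with no time limit on that sentence. Protocol 8.3.2 summarises reasons for leaving the study early but does not list death among them. SAP 6.1.2 tabulates reasons for stopping treatment, which this participant has already done. No passage requires vital status at Week 52 for every randomised participant, including those who leave the study.

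**The case against.** The strongest reply is that the documents are inconsistent rather than empty. Section 4.3, footnote g and a Week 56 EOS together support continued collection of AEs, SAEs and fractures. Protocol 7.3.2 does not stop sites from recording events raised at other times. Appendix 3 assigns AEs before the first extension dose to the main study, without a 60-day limit. Fatal events go to the medical monitor, and a death would normally surface as the reason for leaving the study. The SAP exclusion covers tables and figures, and 6.8.1 separately plans listings of SAEs and all-cause deaths. A 60-day treatment-emergent window is also reasonable: with the mean half-life of 8.77 days in Protocol Table 2, it spans 60 / 8.77 = 6.8 half-lives.

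Most of this stands. It rules out saying that nothing is collected after 60 days, and it makes a death wrongly handled as missing at random possible but unlikely. The 60-day window is sound for its own purpose and should stay.

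Two things are not answered. The passages still give different end dates for the same participant. And whatever sites collect, the late events do not reach the summary comparison between arms; a listing does not replace that comparison.

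**Conclusion.** The point holds as an unreconciled collection rule combined with a definite exclusion from the safety tables. Any last dose at Week 42 or earlier leaves on-study time that the safety comparison does not count, for example about 33 weeks after a Week 10 stop and 17 weeks after a Week 26 stop. This assumes that the participant stays to Week 52 and that the 60-day limits are applied as written. Bias between arms further requires that stopping differs by arm. The documents give no discontinuation rates, so no expected number of lost events can be stated.

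A reader might infer three stronger things, and the documents support none of them:

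- **That there is no collection after 60 days.** Footnote g with EOS at Week 56 supports collection.
- **That an unrelated late death need not be reported to anyone.** The opening sentence of Protocol 7.3.5.2 says otherwise; relatedness governs only whether a death after the reporting period is reported as an SAE.
- **That the bias in the primary result can be sized.** This would need a death rate, the chance that a death goes unrecorded, and the gap between the worst score and the value implied under missing at random. The documents give none of these, and the random coefficient model does not reduce to a simple Week 52 mean.

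What remains for the primary analysis is that its death rule relies on information that no passage requires to be collected.

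**What to change.** 1. **Protocol 3.2.1, 4.3, 6.1.3, 7.3.1, 7.3.5, 7.3.5.2 and Appendix 1 footnote g.** Reconcile these so that, for someone off drug but on study, EOS follows the study calendar (Week 56). Let AE, SAE and fracture collection run to the later of 60 days after the last dose and the last main-study visit, ending at the first extension infusion. The last boundary agrees with Appendix 3.
2. **Vital status.** Record all-cause death to Week 52 for every randomised participant, as consent allows, and name that record in SAP 6.6.1.1.3 as the source for the death rule.
3. **SAP 5.3.1.1 and 6.8.1.** Keep the 60-day treatment-emergent tables. Add on-study tables to Week 52 for all-cause deaths, SAEs, cardiac or pulmonary hospitalisations and fractures.

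The cost is wording in both documents, a few extra tables and a few more background events to record. Participants who remain on study already attend the visits. Sample size and power do not change.
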